9.8. Wisepill

We will continuously monitor Wisepill (Wisepill Technologies, SA) device openings. This electronic monitoring device is a pill box that sends a signal to a secure website via cellular data

networks whenever the device is opened as a proxy for ART adherence. If connection or SIM card problems prevent real-time monitoring, records and diagnostics are stored (up to 1 year) and uploaded to the server when a connection is re-established. The device can store up to a 30-day supply of medication depending on number/size of pills. Since the majority of our participants will be on single-pill, single daily dose ARV regimens, the device will hold a 30-day supply. Wisepill-measured adherence will be operationalized as percentage of days/doses for which a device-opening signal was received in the past month.

9.8.1 Wisepill distribution and instruction.

At the baseline visit, study staff will give the participant a Wisepill device and instruct her/him on how to fill the device, open it for dosing, and re-charge the battery. Before ending this session, study staff will confirm that the Wisepill device is properly set up, that it is recognized by the Wisepill server, and that device openings are being recorded properly (date and time). Participants will be asked to bring the device with them to all study visits. Participants will also be informed that when a participants' device battery gets low, the server will automatically send an SMS to the participant reminding them to charge the device; if 7-days pass after the SMS reminder and the device still appears with a low or flat battery or is not seen at all on the server, study staff will call the participant to remind her/him to charge the battery.

At each subsequent study visit, study staff will ask if the participant is having any problems using Wisepill and will remind her/him to charge the device at least once per month and/or when the red light is blinking. If necessary, devices can be charged in the clinic or the current Wisepill battery can be replaced. Study staff will also conduct a Wisepill test to confirm that the device is properly connecting to the data server. Lastly, study staff will ask participants if her/his ARV medication or dosing schedule has changed since the previous visit and will update this information as necessary. Participants will use the Wisepill Device for four months.

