12. STATISTICAL CONSIDERATIONS

12.1. Overview and General Design Issues

For Aim 2, we will explore whether providing adherence feedback to patients and providers results in changes to patient adherence behavior (as measured by TFV-DP levels, VL, Wisepill use patterns, and self-report) and/or provider behavior with respect to patient management (e.g., requests for additional laboratory tests, calling patient back for an additional appointment, referring patient to an adherence counselor, referring patient to the 'risk of treatment failure clinic'). Below we describe the analytical plan to assess change in patient adherence behavior using Wisepill openings as an example.

This 5-month pilot with a small sample size, will provide preliminary estimates that can be used to inform future power calculations and the design of a larger trial (e.g., estimates of effect size, interclass correlation [ICC] for within individual and within provider/clinic correlation). Using Aim 1 data on self-reported adherence, which includes about 3,000 observations, the mean adherence is 81.96% with a standard deviation of 11.42%. The current plan to recruit 60 subjects and collect their monthly adherence data over the subsequent 4-month period will result in 180 change scores (90 per group) for the Aim 2 analysis. Using the estimated standard deviation from our existing data and assuming the ICC between successive change scores is no greater than 0.20, we will be able to detect a 5.59 percentage point difference in ART adherence between the intervention and control group with 80% power. Assume the mean adherence is about 80% for the control group (very close to what we observed from our observational study in Aim 1), if in truth, the mean adherence is 85.59% (which we optimistically believe is achievable), we have 80% probability to declare the difference of adherence between intervention and control is statistically significant. Therefore, we believe that the data we will collect from 60 participants over the 4-months of follow up will provide adequate power to achieve the study goal.

To generate preliminary estimates of the effect of giving feedback on adherence behavior, we will compare change in average percentage of Wisepill openings (for example) from one month to the next between Feedback and No Feedback (Control) participants.

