Because feedback begins at the first return visit at Month 1 after baseline, each Feedback Group participant will provide up to three change score outcomes (for month $i-1$ to month i for $i=2,3,4$). We will compare these to the corresponding change scores in the Control Group in a generalized linear model (GLM) using generalized estimating equations (GEE) to account for within-subject correlation (ICC) among their three change-scores. The analysis model will include a constant term and the group indicator.

With the limited pilot sample size of 60, we will be able to detect moderately large effects on average improvement in adherence. For example, if the ICC between successive change scores is no greater than 0.20, then the detectable standardized mean difference will be $2.8 * [(2/30) * (1 + 0.2 * (3-1))]^{1/2} = 0.86$, a "large" effect.

Given that this is a pilot study, our ability to explore the role of the moderating variables on adherence-related behavior will be limited. However, looking at the monthly change-scores can reveal important features on which to focus. Moreover, the larger Aim 1 sample (N=250) will provide key data on individual and structural factors affecting adherence, retention, and preferences for sample collection and feedback that we will utilize in multivariable analyses as predictors of DBS TFV-DP levels and Wisepill use patterns. We will also examine these factors as potential effect modifiers in Aim 1 analyses.

For providers we will examine changes in clinical management patterns, for example requests for additional tests or adherence counselling sessions usually only triggered by a raised VL.

Similar to Aim 1, the Baseline and Visit 4 (last visit) Quantitative Assessments will cover a large array of participant information and behaviors that could be potential confounders. To examine how potential confounding factors can influence our statistical analysis, we will first identify a list of variables that is possible be candidates for potential confounding factors and then test whether any of those variables is associated with our outcome (i.e., adherence) and exposure (i.e., the intervention) in our sample. If found, we will include them in the primary analysis model to obtain the adjusted intervention effect. While the official primary analysis will be the one without covariate adjustment, the adjusted analysis will help to interpret the findings from primary analysis.

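### The primary change-score model estimates one third of the Month 1 to Month 4 change, not the difference in adherence level that the plan targets, and makes no use of Months 2 and 3

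*Combined protocol and SAP*

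**What the plan says.** All of this is in section 12.1, except the definition of the adherence measure.

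- **Measure.** Wisepill is the worked example. The aim is to "compare change in average percentage of Wisepill openings (for example) from one month to the next" between arms. Section 9.8 defines Wisepill adherence as the "percentage of days/doses for which a device-opening signal was received in the past month".
- **Outcomes.** "Because feedback begins at the first return visit at Month 1 after baseline", "each Feedback Group participant will provide up to three change score outcomes": the changes from Month 1 to 2, 2 to 3 and 3 to 4. Month 1 is thus treated as the pre-feedback value.
- **Model.** "We will compare these to the corresponding change scores in the Control Group in a generalized linear model (GLM"). "The analysis model will include a constant term and the group indicator", fitted "using generalized estimating equations (GEE) to account for within-subject correlation (ICC) among their three change-scores". No month term, group-by-month term or adherence covariate is listed, and the working correlation is not named.
- **Status.** "While the official primary analysis will be the one without covariate adjustment", a confounder-adjusted version is to help interpret it.
- **Target.** The power text describes a 5.59-point difference between arms as mean adherence of about 80% in controls against 85.59% with feedback. The pilot is also meant to supply effect-size estimates for a larger trial.

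**The concern.** Averaging successive differences removes every intermediate value. What remains is the last month minus the first, divided by the number of intervals. The coefficient then answers a different question from the one in the power text: how fast adherence moved per month between two end points, not how much higher it was while feedback was being given.

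Two things are at stake. A designer of the larger trial who reads the coefficient as the level effect would plan around a figure one third the size of a sustained gain. And a response that appears after the first feedback and fades by Month 4 contributes nothing to the primary coefficient, although the primary objective is to learn how patients behave after feedback.

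**Working it through.** **Inputs from section 12.1.** 30 per arm; three change scores each; ICC at most 0.20 among change scores; SD 11.42 (Aim 1 self-reported adherence); target difference 5.59 points; multiplier 2.8, read as two-sided 5% and 80% power. **Assumed:** SD 11.42 also applies to monthly Wisepill levels, and levels have equal correlation ρ between months. The documents give no value for ρ, so 0.4, 0.6 and 0.8 are shown.

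**1. The plan's own figures.** 2.8 × √[(2/30) × (1 + 0.2 × 2)] = 0.855, the stated 0.86. With 90 change scores per group, 2.8 × √[(2/90) × 1.4] × 11.42 = 5.64, close to the stated 5.59. (The two figures do not agree with each other: 0.86 × 11.42 = 9.8 points. That is a separate matter. The 5.59 is used below because the plan translates it into 80% against 85.59%.)

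**2. What the coefficient is.** Let Yk be adherence in month k. With complete data and an independence or exchangeable working correlation, the group coefficient is the arm difference in the mean of

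[(Y2 − Y1) + (Y3 − Y2) + (Y4 − Y3)]/3 = (Y4 − Y1)/3.

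Fitted GEE models on simulated data for 60 participants matched this contrast to about 1e-15.

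**3. What it returns when the largest gain is 5.59 points.**

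| Gain at Months 2, 3, 4 | Monthly changes | Planned coefficient | Months 2–4 average |
|---|---|---|---|
| 5.59, 5.59, 5.59 (sustained) | +5.59, 0, 0 | 1.86 | 5.59 |
| 5.59, 5.59, 0 (fades) | +5.59, 0, −5.59 | 0 | 3.73 |
| 1.86, 3.73, 5.59 (even ramp) | +1.86 each | 1.86 | 3.73 |
| 0, 2.80, 5.59 (late onset) | 0, +2.80, +2.80 | 1.86 | 2.80 |

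For the coefficient itself to equal 5.59, the Month 4 gain would have to be 3 × 5.59 = 16.77 points.

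An AR(1) working correlation between −0.5 and 0.2 moves the sustained figure to between 1.60 and 2.00 and leaves the fading figure at zero. With 10% dropout, the simulated means were 1.93 (sustained) and 0.20 (fading).

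**4. Power for a sustained gain.** Multiplying the planned coefficient by 3 leaves its test unchanged, so both analyses can be put on the scale of the gain.

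- Planned: variance of Y4 − Y1 = 2(1 − ρ) × SD².
- Alternative (mean of Months 2–4, adjusted for Month 1): variance = [(1 + 2ρ)/3 − ρ²] × SD².
- SE = √[(2/30) × variance]; power = Φ(effect/SE − 1.96).

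| ρ | Planned SE | Planned power | Adjusted SE | Adjusted power | Variance ratio |
|---|---|---|---|---|---|
| 0.4 | 3.23 | 41% | 1.96 | 82% | 2.73 |
| 0.6 | 2.64 | 56% | 1.80 | 87% | 2.14 |
| 0.8 | 1.86 | 85% | 1.40 | 98% | 1.76 |

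If the correlation of levels instead decays as AR(1) with parameter 0.4, 0.6 or 0.8, power is 28%, 33% or 48% for the planned model against 76%, 74% or 84%.

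**5. Other shapes, same SEs.** The planned power depends only on the Month 4 gain.

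- Fading: planned 5% throughout. The adjusted effect is 3.73, so at ρ = 0.6, Φ(3.73/1.80 − 1.96) = 54% (48% at ρ = 0.4, 76% at ρ = 0.8).
- Even ramp: the adjusted effect is again 3.73, giving 48%, 54% and 76% against planned 41%, 56% and 85%.
- Late onset: the adjusted effect is 2.795, so at ρ = 0.6, Φ(2.795/1.80 − 1.96) = 34% against planned 56%; at ρ = 0.8, 51% against 85%.

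**The case against.** The strongest reply is that a mean monthly change is a legitimate quantity and the plan names it as such. Three times the coefficient is an unbiased Month 4 minus Month 1 contrast with the same p-value. Feedback is given at Months 1, 2 and 3, so a cumulative response is plausible, and an end-point contrast suits that shape. For TFV-DP, with a half-life of about 17 days, a gradual rise is likely even after an abrupt change in behaviour. This is also a 60-person pilot with several exploratory measures.

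Most of that stands, and it limits the point. It does not remove the mismatch with the plan's stated target, which is a level difference.

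Four stronger readings are tempting, and the documents do not support them:

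- *The estimate is biased or two thirds of the information is lost.* The factor of three is scale. The real loss is that Months 2 and 3 go unused.
- *The missing pre-feedback covariate causes the cancellation.* Month 1 already enters, by subtraction. Adding it as a covariate to the change-score model would leave the cancellation in place.
- *The trial cannot see a transient response.* Section 12.1 also expects to look at the monthly change scores, where a fading gain would show as a rise and then a fall. That look is informal and leaves the primary coefficient unchanged.
- *True power is about 15%.* Entering 1.86 with the plan's SD of 11.42, ICC of 0.20 and 90 scores per group gives 15%. But equally correlated levels make adjacent changes correlate at −0.5, not +0.20, so this figure belongs to those inputs and not to the design.

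**Conclusion.** The point holds as a mismatch between the primary estimator and the stated target. The telescoping is exact for complete data under an independence or exchangeable working correlation, and nearly so with modest dropout. It needs no assumption about variances. The plan powers for 5.59 points of level, and the primary coefficient would report that gain, if sustained, as 1.86 and a gain lost by Month 4 as zero.

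The power comparison is less certain. It rests on a self-report SD carried over to Wisepill and on assumed correlations. Across those assumptions the level-based analysis is clearly better for sustained and fading gains and worse for late-onset ones; for an even ramp it is slightly better at ρ = 0.4 and worse at 0.6 and 0.8. Because the plan's own target is a level difference, this is more than a matter of taste. It should be changed before analysis, but it does not invalidate the pilot.

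**What to change.** - **Primary analysis.** Fit a repeated-measures model (GEE is fine) to Wisepill percentage at Months 2, 3 and 4, with group, visit and pre-feedback Wisepill percentage as a covariate. Section 9.3 sends results to providers before the monthly visit, so define the covariate as Month 1 or as the part of Month 1 before the first provider message. Name the working correlation.
- **Reporting.** Give the Months 2–4 average group difference as the primary estimate and the month-specific differences descriptively. Keep the change scores as description.
- **Power text.** Restate both calculations in section 12.1 for this estimand. They now rest on 180 change scores and on an ICC among change scores, and neither carries over.

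No new data are needed, since Wisepill openings are recorded continuously. The cost is the rewriting, together with lower power for a late-onset gain (34% against 56% at ρ = 0.6) and, when the correlation is high, for a gradual one (76% against 85% at ρ = 0.8 for an even ramp). In both cases the average also reports less than the final gain; the month-specific differences would show that pattern.

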9.3. Monthly Follow Up Visits (Study Visits 1-3)

The following procedures/assessments will be performed at every visit:

1. Study staff will verify the patient by the name on the record;
2. Study staff will obtain blood samples for the following: DBS, and 5ml venous blood for VL storage (See Standard Operating Procedure (SOP) C002 BLOOD SPECIMEN ACQUISITION, PROCESSING AND STORAGE GUGULETHU RESEARCH OFFICES (GRO) for additional details);
3. Study staff will assess **self-reported adherence**, measure weight and assess pregnancy status (women only);
4. Study staff will conduct a **Wisepill** device functionality test and will check in with the participant regarding any time(s) participant took a dose without using Wisepill, and resolve any issues;
5. Study staff will update ARV regimen, dosing time(s), and HIV care provider and clinic contact information;
6. In the Feedback arm only: Study staff will use the protocols and materials developed with the FDWs to explain to the participant the results from the previous month's DBS. This will not be an intensive adherence counseling session, but an opportunity to ensure that the participant understands the feedback. If necessary, participants will be referred to an adherence counselor for further support.
7. Study staff will update the **Locator Form**;
8. Study staff will give the **participant compensation**;
9. Study staff will schedule the next month visit.
10. In the Feedback arm only: Providers will receive monthly DBS drug level results for participants randomized to the Feedback study arm, prior to the participant's monthly visit. Results will be shared according to the protocol developed by the FDW.

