9.7.2 Visit 4 Quantitative Assessments

The Visit 4 Quantitative Assessment is a reduced version of the Baseline Quantitative Assessment. It will include a briefer battery of socio-demographic, medical history, social support or medication beliefs assessments. It will more focus on mental health, substance use, medication social support and life events. The Visit 4 Quantitative Assessment will encompass the Exit Interview and will take approximately 1 hour to complete.

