9.7.3. Exit interview

Study staff will administer a semi-structured Exit Interview during the Visit 4 Quantitative Assessment to all study participants. Feedback arm participants will be asked about their understanding and perceptions of the meaning of the drug-level feedback, whether (and if so how) the feedback from the study staff and/or providers influence participants' behavior (e.g., medication-taking, disclosure to people in their social network, seeking adherence support, etc.). No feedback arm participants will be asked about if/how they would like to receive feedback if this was put into routine clinical practice (e.g., from a lay HCW, from a doctor, by SMS).

In both cases, the Exit Interview assessment will include closed and open-ended questions exploring the patient's thoughts about receiving DBS-based feedback.

9.7.4. Self-Reported Adherence Questionnaire.

Study staff will assess self-reported adherence in the past 30 days at every visit. The Self-Reported Adherence Questionnaire will take approximately 3 minutes to complete.

9.7.5. Pregnancy Status.

At each study visit, study staff will ask study participants (women only) whether they are currently pregnant or plan to become pregnant.

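### Section 12.1 lets Visit 4 variables, measured after feedback, enter the supportive adjusted model if they are associated with both adherence and arm, which could bias the adjusted effect in either direction

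*Combined protocol and SAP*

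**What the plan says.** Section 12.1 names one source for candidate covariates, covering both time points: "the Baseline and Visit 4 (last visit) Quantitative Assessments will cover a large array of participant information and behaviors that could be potential confounders". The team first draws up a list of candidates and will then "test whether any of those variables is associated with our outcome (i.e., adherence) and exposure (i.e., the intervention) in our sample". For those that pass, "If found, we will include them in the primary analysis model to obtain the adjusted intervention effect". The status of the result is clear: "While the official primary analysis will be the one without covariate adjustment, the adjusted analysis will help to interpret the findings from primary analysis". Nothing in the section limits the list to values taken before feedback starts.

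On timing, Table 1 (schedule of events) places drug-level feedback at Months 1, 2 and 3 and the Visit 4 assessment at Month 4. Section 12.1 says that "each Feedback Group participant will provide up to three change score outcomes", ending at Months 2, 3 and 4. Allocation is 1:1 at random (section 12.4).

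On content, section 9.7.2 says of the Visit 4 assessment: "It will more focus on mental health, substance use, medication social support and life events". Section 9.7.3 has the Exit Interview ask Feedback participants whether feedback influenced behaviours such as "medication-taking, disclosure to people in their social network, seeking adherence support, etc". The Feedback-arm step in section 9.3 adds: "If necessary, participants will be referred to an adherence counselor for further support". Section 14.5.1 lists distress on learning one's drug level as a possible harm.

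**The concern.** In a randomised trial a baseline variable can differ between arms only by chance. A variable measured after feedback can differ by chance or because feedback moved it. Requiring an association with arm therefore makes the screen more likely to pick a variable that feedback has affected, and the further requirement of an association with adherence makes it more likely that the variable lies on the path to adherence or results from it.

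The order in time points the same way. Two of the three change scores end at Months 2 and 3, roughly one to two months before Visit 4. Unless a Visit 4 item has a recall period that reaches back, which is not stated, a time-varying score cannot be a cause of those changes and may be a result of them. Stable items such as education are not affected.

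The bias has no fixed sign. If feedback raises support and support goes with better adherence, adjusting for Visit 4 support makes feedback look weaker. If feedback worsens mental health and worse mental health goes with a smaller gain, adjusting makes feedback look better than its total effect. In both cases a reader comparing the adjusted and unadjusted results could take the gap for confounding.

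**Working it through.** The plan gives no figure for this point, so there is none to reproduce. The calculation below shows what the rule does under stated assumptions.

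**Inputs from the documents**
- 30 per arm (section 12.4) and at most 10% dropout (section 12.6): 30 × 0.9 = 27 per arm.
- SD of self-reported adherence levels 11.42 points (section 12.1).
- Three change scores per participant (section 12.1).

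**Assumptions (not in the documents)**
- D: effect of feedback on a Visit 4 score, in SD.
- r: within-arm correlation of that score with the mean adherence change.
- A two-sided 5% threshold for each test.
- ρ: correlation of Month 1 with Month 4 adherence.

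**Step 1. Shift caused by adjusting.** The unadjusted model estimates the total effect τ. With the score added, the arm coefficient estimates τ − D × r. For D = 0.5 and r = 0.3 the shift is 0.5 × 0.3 = 0.15 SD: downward if D and r have the same sign, upward if they differ.

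**Step 2. In percentage points.** With complete data the mean of three successive changes is (Month 4 − Month 1)/3. Its SD is 11.42 × √(2(1 − ρ))/3, which is 4.50, 3.81 and 2.95 for ρ = 0.3, 0.5 and 0.7. So 0.15 SD is 0.68, 0.57 and 0.44 points. This borrows a self-report SD; none is given for Wisepill.

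**Step 3. How often the score is admitted.** Simulation: 27 per arm, τ = 0, 40,000 trials per row. The score is admitted when a t-test by arm and its correlation with the outcome both reach p < 0.05. The expected shift counts a trial that does not admit the score as zero.

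| D | r | Admitted | Expected shift (SD, absolute) |
|---|---|---|---|
| 0 | 0.3 | 3% | 0.00 |
| 0.1 | 0.3 | 4% | 0.01 |
| 0.3 | 0.2 | 6% | 0.01 |
| 0.3 | 0.3 | 12% | 0.03 |
| 0.5 | 0.3 | 25% | 0.07 |

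The last row exceeds 0.25 × 0.15 = 0.04 because admitted trials are also those with a larger chance imbalance in the score. With a 10% threshold that row becomes about 39% and 0.10 SD. With τ = 0.3 SD it becomes about 31% and 0.08 SD, downward.

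**Step 4. Reading the table.** At r = 0.3, a score moved by 0.5 SD is admitted about eight times as often as one that feedback does not touch (25% against 3%). The rule thus selects for the variables that should stay out.

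**Step 5. Comparison with precision.** The 95% half-width for the difference between arms is about 1.96 × √(2/27) = 0.53 SD, so an expected shift of 0.07 SD is small beside the pilot's own uncertainty.

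**The case against.** The strongest reply is that little hangs on this. The unadjusted model is declared primary and contains only a constant and the group indicator, and the preliminary effect estimate for a larger trial comes from that comparison. This stands. A reader might infer that the pilot's main estimate is biased; the documents do not support that.

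A reader might also infer that any Visit 4 score differing by arm goes into the model. It does not: association with adherence is required too, and the team draws up a candidate list before testing. No Visit 4 covariate is named, and a sensible list might contain none. That makes the problem possible rather than certain. It does not remove it, because the written rule names Visit 4 as a source.

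A third tempting reading is that the protocol expects feedback to change these domains. It is more guarded: the Exit Interview asks whether feedback had an influence, referral is only as needed, and distress is something that may occur, with the assessment questions themselves given as another cause. Linking support-seeking or counselor referral to the medication social support measure is an inference, since that instrument is not described.

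Finally, D and r are invented. With D = 0.1 admission is hardly above the 3% seen with no effect on the score. At the other end, D = 0.8 with r = 0.5 would give 78% admission and an expected shift of 0.35 SD, but nothing in the documents supports values of that size, and the conclusion does not use them.

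**Conclusion.** The rule is wrong as written, with a limited consequence. By pooling Baseline and Visit 4 variables and selecting on association with both adherence and arm, section 12.1 allows possible consequences of feedback to be adjusted for as if they were confounders. The harm is confined to the supportive adjusted analysis and to what is read into its gap from the primary result. The illustrative size is a 0.15 SD shift from adjusting, with admission in about 25% of trials, assuming D = 0.5, r = 0.3, a 5% screen and 27 per arm. With smaller effects the shift is negligible. Neither the direction nor the size can be fixed from the documents. This is a point to consider, not a threat to the trial's main result.

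**What to change.** Add one sentence to section 12.1: candidate covariates for the adjusted model are Baseline values only, and Visit 4 scores are excluded from it and may be described by arm. The separate use of Visit 4 medical history to interpret drug levels (section 9.9.1.1) can stay.

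This needs no new data, visits or procedures. The cost is that a post-baseline event unrelated to feedback but unbalanced by chance, such as a life event, would no longer be adjusted for; describing it by arm covers most of that need. Baseline candidates would still be tested against arm, where differences arise only by chance. Choosing a short list of prognostic Baseline variables in advance and dropping that test would be tidier, but is not needed to settle this point.

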14.5 Social Impact Events

Participants enrolled in the study may experience personal problems resulting from the study participation. Such problems are termed social impact events and could potentially include the following:

14.5.1 Psychological distress.

Participants may experience psychological distress resulting from the assessment questions or from learning the amount of TFV-DP drug concentration in the previous month. Using strategies established in our previous SA and US studies, and in Aim 1 the following steps will be taken to minimize the risk of psychological distress resulting from assessment questions.

1. Participants will be informed that the assessments include questions about sensitive behaviors (e.g., mental health, drug use, non-adherence), and that they can decline to answer any questions with which they are uncomfortable.
2. Procedures for emergency and nonemergency situations will involve the interviewer informing the SA SCO of any such incidents of distress so that s/he can monitor compliance with distress-related protocol.
3. Participants who experience mild to moderate distress will be referred to the clinic mental health staff for counseling. Because the study will take place at the GRO based at the Hannan Crusaid Treatment Centre, we will be able to make immediate referrals as needed to health care providers.

14.5.2 Unintended disclosure.

We will take steps to minimize inadvertent disclosure of HIV status from receipt of text message reminders to charge Wisepill by keeping the text message simple and without any identifying and/or status related information; the message reads, "Please charge your ibhokisi (box)".

14.5.3 Confidentiality breach.

Although study sites will make every effort to protect participant privacy and confidentiality, it is possible that participants' involvement in the study, or information collected by the study, could become known to others, and that participants may experience stigmatization or discrimination as a result. We will take the following steps to protect against the risk of a confidentiality breach.

1. All data, including blood and DBS samples, assessment, Wisepill output, and participant files will be labeled only with study identification numbers, and no participant names will be attached to study data.

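### The supportive adjusted analysis may adjust for Visit 4 variables that feedback itself has changed, which can bias the adjusted effect in either direction

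*Combined protocol and SAP*

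**What the plan says.** Section 12.1 states that the "Baseline and Visit 4 (last visit) Quantitative Assessments will cover a large array of participant information and behaviors that could be potential confounders". A candidate list is to be drawn up first. The team will then "test whether any of those variables is associated with our outcome (i.e., adherence) and exposure (i.e., the intervention) in our sample", and variables that pass enter the primary model to give an adjusted effect. No test level is stated, and neither this section nor any other restricts the list to baseline.

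On status, the section says that "the official primary analysis will be the one without covariate adjustment, the adjusted analysis will help to interpret the findings from primary analysis".

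On timing, the same section says: "Because feedback begins at the first return visit at Month 1 after baseline, each Feedback Group participant will provide up to three change score outcomes". Table 1 places feedback at Months 1, 2 and 3, and the Visit 4 assessment at Month 4. Section 9.7.2 says of that assessment: "It will more focus on mental health, substance use, medication social support and life events". Allocation is randomised 1:1, 30 per arm (section 12.4).

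**The concern.** Confounding of a randomised comparison needs a difference between arms that exists before the intervention acts. For baseline variables, randomisation leaves only chance differences. A Visit 4 variable is measured after three rounds of feedback. It is also measured no earlier than the end of every change-score interval, since Wisepill adherence covers the past month (section 9.8) and the last interval ends at Month 4. If such a variable differs systematically by arm, the difference arose after randomisation. If it is also linked to adherence, it may lie on the path from feedback to adherence, be a result of adherence, or share an unmeasured cause with adherence. In none of these cases does adjusting for it remove confounding. It removes or distorts part of the effect being estimated.

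The protocol itself allows for such paths, with different signs. Section 14.5.1 says: "Participants may experience psychological distress resulting from the assessment questions or from learning the amount of TFV-DP drug concentration in the previous month". Section 9.7.3 asks whether feedback influenced "medication-taking, disclosure to people in their social network, seeking adherence support". Section 9.3 adds, at the feedback step: "If necessary, participants will be referred to an adherence counselor for further support".

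The adjusted result is meant to help interpret the primary one. An adjusted effect near zero could be read as showing that a real effect was confounding. An enlarged one could be read as confirmation.

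**Working it through.** **1. Inputs.** From the documents: 30 per arm, and three successive change scores per participant. The documents give no size for the effect of feedback on any Visit 4 variable, no correlation of such a variable with adherence, and no test level, so these are assumed. The plan's own figures (a 5.59-point and a 0.86 SD detectable difference) do not bear on this point and are not used.

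**2. Unit.** Set the within-arm SD of a participant's mean monthly change to 1. The standard error of the arm difference is then sqrt(2/30) = 0.258 SD.

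**3. Closed form.** Let d be the true effect, a the shift (in SD) that feedback causes in the Visit 4 variable, and r the within-arm correlation of that variable with adherence change. Then

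adjusted effect = d − a·r.

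This holds whatever the reason for r, as long as the slope is the same in both arms. For a pure consequence of adherence, a = r·d, so the adjusted effect = d·(1 − r²).

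| Assumed case | Move in the effect | Calculation |
|---|---|---|
| Small, either sign (a 0.1–0.3, r 0.2–0.3 in size) | 0.02 to 0.09 SD | 0.1×0.2 to 0.3×0.3 |
| Larger, same sign (a 0.5, r +0.5) | −0.25 SD | −0.5×0.5 |
| Larger, opposite sign (a 0.5, r −0.5) | +0.25 SD | −0.5×(−0.5) |
| Consequence, r 0.3 / 0.5 / 0.7 | effect × 0.91 / 0.75 / 0.51 | 1 − r² |

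With no true effect (d = 0), the two larger cases give adjusted effects of −0.25 and +0.25 SD.

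**4. How often the rule keeps the variable.** This was simulated with 20,000 trials per setting and d = 0.25, 0.50 or 0.75. A variable was kept if p < 0.05 for both its association with arm and its association with adherence change.

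| Case | Kept in |
|---|---|
| Small | 1–18% of trials |
| Larger, same sign | 47–48% |
| Larger, opposite sign | 37–45% |
| Consequence, r 0.3 / 0.5 / 0.7 | 4–12% / 7–30% / 11–52% |
| Prognostic baseline variable (a = 0, r 0.3–0.7) | about 3–5% (7–10% at a 10% test level) |

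**5. Bias against the truth.** Take a 0.5, r +0.5 and d 0.50. In the trials that keep the variable, the unadjusted estimate averages 0.61 and the adjusted one 0.25. Of the 0.36 gap, 0.61 − 0.50 = 0.11 is chance imbalance picked out by the selection rule, and 0.50 − 0.25 = 0.25 is bias. For baseline variables, selection and adjustment move the average estimate by no more than 0.004 SD.

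**The case against.** The strongest reply is that little depends on this. The plan fixes the unadjusted model as primary, the trial is a pilot, and a reader who sees both results can see any movement. That stands, and it limits the consequence to how the adjusted result is used. It does not make that result a valid adjusted effect, which is the role the plan gives it.

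Second, the list is unwritten, and the team could remove post-feedback variables when drawing it up. That is also true: adjustment for Visit 4 variables is permitted and signalled, not certain. But the section names Visit 4 as a source, and its selection rule does not screen such variables out.

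Third, some of the supporting text does not identify a testable covariate. The Exit Interview questions on how feedback influenced behaviour go to the Feedback arm only, and counselor referral is a visit procedure, not an assessment item. The distress statement is a risk warning that also covers the questionnaires both arms complete. These passages show that the protocol allows for feedback to change behaviour or mood. The candidate covariates themselves come from the Visit 4 domains, chiefly mental health and medication social support. Life events outside the study's influence differ by arm only by chance and are not at issue.

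Fourth, a 0.5 SD shift may be generous, since section 9.3 says the feedback session is not intensive counselling. If the shift and the correlation are small, so is the bias.

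**Conclusion.** The concern holds. As written, the rule allows the supportive analysis to adjust for effects of feedback, and it selects for them. The direction of the bias depends on the sign of the path. Its size runs from 0.02–0.09 SD in the small case to 0.25 SD, about one standard error of the arm comparison, in the larger one. These figures rest on assumed shifts, correlations and a 5% test level, because the documents supply none. The direction of the argument needs only randomisation and the timing of Visit 4.

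The test against arm raises a separate point for baseline variables. It causes essentially no bias there, but it discards a useful prognostic covariate in roughly 95% or more of trials at the 5% level. That is a loss of efficiency. The primary analysis is not affected by either point.

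**What to change.** In section 12.1, limit covariates for the adjusted intervention effect to a short, prespecified list of baseline variables that are already collected and expected to predict adherence change. The sponsor should choose them. Drop the test of association with arm. State that Visit 4 variables enter only a separately labelled exploratory or mediation analysis, whose estimate is not presented as a confounder-adjusted effect.

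This changes wording only and needs no new data. The primary analysis, the sample size and the use of Visit 4 comorbidities in modelling drug-level variability (section 9.9.1.1) stay as they are. Each covariate term costs one degree of freedom in a 60-person trial, so the list should be short.
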